7.5 Safety Analysis

7.5.1 Extent of Study Drug Exposure

Study drug exposure will be summarized by study phase (based on Section 7.1) and for the entire study for the Safety Analysis Set including:

- Duration of treatment (weeks), calculated as (last dose date first dose date + 1)/7
- Total number of tablets/capsules taken, calculated as total number of tablets/capsules dispensed total number of tablets/capsules returned
- Total dosage taken, calculated as total number of tablets taken * 20mg/tablets (or total number of capsules taken *10 mg/capsules)
- Weekly average dose (mg/week) received defined as total dosage taken (mg)/duration of treatment (weeks)
- Compliance (%), calculated as total dosage taken/sum of (planned dosing regimen * regimen period (days)) * 100.

Study drug administration, study drug regimen, overall study drug exposure and study drug compliance will be listed for the Safety Analysis Set.

7.5.2 Adverse Events

Adverse events (AEs) will be coded using MedDRA version 23.0 or higher and will be classified by SOC and PT of MedDRA. The coding may be updated according to newly released versions of the dictionary. Severity of AEs will be graded according to Common Terminology Criteria for Adverse Events (CTCAE) v5.0.

A treatment emergent adverse event (TEAE) is defined as any AE that occurs after administration of the first dose of study drug.

AEs are classified as related or not related to the study drug based on investigator assessment. AEs with missing or unknown relationship to the study drug will be considered as related AEs.

TEAEs with starting date prior to the first dose date in the Open Label Extension Phase will be classified as TEAEs in the Core Phase. TEAEs with starting date on or after the first dose date in the Open Label Extension Phase will be classified as TEAEs in the Open Label Extension Phase. An overall summary of TEAEs will be provided for each phase and the entire study including:

• Any TEAE

- Any related TEAE
- Any Grade 3-5 TEAE
- Any TEAE leading to study discontinuation
- Any TEAE leading to drug withdrawn
- Any TEAE leading to dose reduction/interruption
- Any serious TEAE
- Any serious TEAE by relationship to study drug (related, unrelated)
- Any death
- Any AESI (AE of special interest) (Thromboembolic events, CTCAE Grade ≥3 Bleeding events)

The following events will be tabulated and summarized. The output will be sorted by decreasing frequency of PT within SOC which is sorted alphabetically in overall events.

- TEAEs by SOC and PT
- TEAEs by PT
- Drug-related TEAEs by SOC and PT
- Drug-related TEAEs by PT
- TEAEs by maximum toxicity grade, SOC and PT
- TEAEs leading to study discontinuation by SOC and PT
- Serious TEAEs by SOC and PT
- Drug-related serious TEAEs by SOC and PT
- AESIs by AESI category and PT

Two categories for Adverse Events of Special Interest (AESI) will be summarized and are defined based on terms in Standardized MedDRA Queries (SMQs) from MedDRA v26.1 or later:

- Thromboembolic events Any thrombotic or embolic event, whether arterial or venous SMQ = Embolic and thrombotic events
- Bleeding Events Any clinically significant blood loss [e.g., bleeding events with CTCAE grade 3+ (based on AE severity [AESEV]>=3] - SMQ = Haemorrhage terms (excl laboratory terms)

If a SOC or PT is reported more than once for a subject, the subject will be counted only once in the incidence for that SOC or PT.

The following listing will be provided for the Safety Analysis Set:

- AEs
- Serious TEAEs

- Death
- Grade 3-5 TEAEs
- TEAE leading to study discontinuation
- AESIs

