7 STUDY TREATMENTS

7.1 Treatment Groups

The 12 week Core Phase of this Phase 3b study is randomized, double-blind, and placebo-controlled. At Day 1/Visit 2, subjects will be randomized in a 3:1 ratio to receive either avatrombopag or matching placebo.

The Extension Phase of this study is open-label therefore all subjects will receive avatrombopag.

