2.2 Sample Size Determination

The proposed sample size is based on the anticipated response rates for avatrombopag and placebo for the primary endpoint (durable response) and the key secondary endpoint (platelet response for 2 consecutive weeks).

Based on the eltrombopag PETIT2 study conducted in pediatric patients with chronic ITP, the durable response rates were 41.3% and 3.4% for eltrombopag and placebo, respectively (Grainger, 2015). It is reasonable to assume that the treatment effect of avatrombopag will be very similar to that of eltrombopag, due to both drugs being in the same class, having similar mechanisms of action, and treating similar patient populations (e.g., patients aged ≥ 1 to <18 years with relapsed or refractory disease after 1 or more previous treatments for ITP and a Baseline platelet count $<30\times10^9$ /L). With the 3:1 ratio of avatrombopag to placebo, a total of 72 subjects (54 avatrombopag and 18 placebo) will provide at least 90% power to detect a treatment difference of 37.9% in durable response at α =0.05, based on the Fisher's exact test.

In addition, a 12 week study of romiplostim in treating pediatric ITP patients showed that 88% of romiplostim treated subjects achieved a platelet count $\geq 50 \times 10^9 / L$ for 2 consecutive weeks (key secondary endpoint), whereas none of the placebo treated subjects achieved the same endpoint (Bussel, 2011). With the 3:1 ratio of avatrombopag to placebo, a total of 72 subjects (54 avatrombopag and 18 placebo) will provide $\geq 99\%$ power to detect a treatment difference of 80% in proportion of subjects achieving a platelet count $\geq 50 \times 10^9 / L$ for 2 consecutive weeks at $\alpha = 0.05$, based on the Fisher's exact test.

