2.3 Randomization and Blinding

During Day 1/Visit 2 of the Core Phase, after study eligibility has been confirmed, randomization assignment will be performed using interactive response technology (IRT). Randomization will be stratified by age cohort. Subjects will also be stratified by a baseline platelet count of $\leq 15 \times 10^9/L$ or $>15 \times 10^9/L$ to $<30 \times 10^9/L$ in order to ensure treatment groups are approximately balanced. Following randomization, study drug will be dispensed in a double-blind manner. The Sponsor, the subject, and the clinical site personnel will be blinded to the treatment assignment.

No randomization or blinding is necessary for the Extension Phase as all subjects will receive open-label avatrombopag.

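### The entire-study exposure and TEAE summaries start at first study drug, so placebo weeks, nominal placebo milligrams and placebo-period events of the 18 placebo children are carried into them

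*SAP*

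**What the plan says.** SAP 7.5.1 sets the exposure output: "Study drug exposure will be summarized by study phase (based on Section 7.1) and for the entire study for the Safety Analysis Set including" a list of measures. Duration is last dose date minus first dose date plus one, in weeks. The dose formula makes no exception for placebo units: "Total dosage taken, calculated as total number of tablets taken * 20mg/tablets", with 10 mg for each capsule. Weekly average dose divides that total by duration.

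SAP 7.5.2 sets the TEAE overview: "An overall summary of TEAEs will be provided for each phase and the entire study". Its anchor is study drug: "A treatment emergent adverse event (TEAE) is defined as any AE that occurs after administration of the first dose of study drug".

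In the Core Phase, study drug is either product. Protocol 7.1 says "subjects will be randomized in a 3:1 ratio to receive either avatrombopag or matching placebo", and SAP 2.3 says "Following randomization, study drug will be dispensed in a double-blind manner". In the Extension Phase every child takes avatrombopag.

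SAP 7.1 gives table columns for the Core Phase (by treatment, within cohort and overall) and for the Extension Phase (by cohort and overall), but none for the entire study. SAP 6.4 and 6.5 define a safety set for each phase, but none for the entire study.

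**The concern.** A child randomised to placebo who moves into the Extension Phase has two periods: up to 12 weeks on placebo, then avatrombopag. The entire-study rules run them together. The child's treatment duration includes placebo weeks, the total dosage includes milligrams of avatrombopag never taken, and the TEAEs include events that began on placebo.

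The choice of columns does not remove this. A single pooled column mixes placebo with drug across all children. Columns by randomised arm keep the avatrombopag arm clean, but the placebo column then holds placebo time followed by up to two years of avatrombopag. Neither layout describes experience on avatrombopag in all children who received it, which is what a reader would most naturally look for in an entire-study table.

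**Working it through.** **Inputs.** Placebo children: 7 + 7 + 4 = 18, against 21 + 21 + 12 = 54 on avatrombopag (SAP 2.1), which matches the 54 and 18 in SAP 2.2. As a check on that source, the exact power of the two-sided Fisher test for 41.3% against 3.4% with 54 and 18 children is 94.5%, consistent with the stated minimum of 90%. Core Phase: 12 weeks, 84 days. Extension Phase: 2 years. Starting doses and titration steps: Protocol Tables 2 to 4. The documents give no entire-study exposure figure to reproduce.

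**Placebo subject-weeks.** If all 18 complete the Core Phase: 18 × 12 = 216, out of 72 × 12 = 864 Core weeks (25%).

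**Share of entire-study exposure.** Let E be mean Extension weeks over all 72 children (assumed; non-entrants count as zero). Share = 216 / [72 × (12 + E)].

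- E = 13 (3 months): 216 / 1,800 = 12.0%
- E = 26 (6 months): 216 / 2,736 = 7.9%
- E = 52 (12 months): 216 / 4,608 = 4.7%
- E = 104 (full follow-up): 216 / 8,352 = 2.6%

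The shorter values are relevant because SAP 5.3 locks the database when the last child finishes the Core Phase and analyses whatever Extension data are then available. For one placebo child with 26 Extension weeks, 12 / 38 = 31.6% of the recorded duration is placebo.

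**Early exit.** Protocol 5.3 lets children leave the Core Phase for lack of effect. As an illustration, two weeks at the starting level, two at level 5 and three at level 6 make 7 weeks. If all 18 left then: 18 × 7 = 126 placebo weeks. Share = 126 / [54 × 12 + 126 + 72 × E]: 4.8% at E = 26 (126 / 2,646) and 2.8% at E = 52 (126 / 4,518).

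**Nominal placebo dose, Cohort 1 or 2.**

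- Starting dose for 84 days: 20 × 84 = 1,680 mg
- Fastest up-titration, 12 weeks: 2 × 140 + 2 × 200 + 8 × 280 = 2,920 mg
- Same titration, exit at week 7: 2 × 140 + 2 × 200 + 3 × 280 = 1,520 mg

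The second figure needs 8 weeks at level 6. Table 3 stops study drug for counts below 30×10⁹/L after 3 weeks at the maximum, so that child's counts would have to stay at 30 or above but below 50×10⁹/L. It is an upper bound.

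All 18 at starting doses for 84 days: 14 × 84 × 20 + 4 × 84 × 10 = 26,880 mg, out of 56 × 84 × 20 + 16 × 84 × 10 = 107,520 mg (25% of nominal Core milligrams).

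**TEAEs.** SAP 7.1 and 7.5.2 report numbers and percentages of subjects. If all 72 enter the Extension Phase, each placebo child whose only event of a given type began on placebo adds 1/72 = 1.4 percentage points to a pooled percentage. A placebo child who never enters stays in the denominator without any avatrombopag exposure, and also in the numerator if an event occurred. The first effect can only raise the percentage; the second can move it either way. The documents give no paediatric event rates from which to size the net change.

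**The case against.** The SAP calls the measure study drug exposure, not avatrombopag exposure, and study drug includes placebo, so the label is literally correct. Protocol 11.2.3 has safety summarised by treatment group, and SAP 6.4 groups the Core safety set by the drug actually received. Table shells are not in the documents, so a single pooled column is only one possibility. The default in SAP 7.1 is to summarise by phase, and TEAEs are assigned to a phase by the first Extension dose date. Core tables therefore separate placebo from drug, and Extension tables contain only avatrombopag.

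Most of that stands and limits the scope. It does not remove the point: a placebo child who crosses over has received both products, so neither treatment group nor drug actually received says where that child's entire-study weeks and events belong. Calling the measure study drug exposure also does not explain milligrams credited for placebo tablets.

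A reader might infer that long-term event rates are distorted in both numerator and denominator. The documents do not support that. No exposure-adjusted rate is planned, so the person-week shares apply to the exposure summary and not to any TEAE statistic. Placebo children who do enter the Extension Phase belong in the avatrombopag-exposed denominator.

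**Conclusion.** The point holds as a minor one, confined to the entire-study exposure summary and the entire-study TEAE overview. As written, these carry Core placebo weeks, nominal milligrams and events for 18 of 72 children, with either a pooled or a by-arm layout.

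The 216 subject-weeks are a maximum that assumes all 18 complete the Core Phase; the 126 weeks for a week-7 exit are an illustration. The shares of 2.6% to 12% rest on 216 weeks and on assumed mean Extension times that the documents do not give. The per-child dose of 1,680 mg assumes 84 days at the Cohort 1–2 starting dose. A reader should not take 216 weeks or 2,920 mg as expected values.

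Nor should the point be read as a threat to the randomised comparison, the primary efficacy test or the per-phase safety tables. None of them uses the entire-study rules.

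**What to change.** In SAP 7.5.1 and 7.5.2, define the entire-study summaries as an avatrombopag-exposed summary:

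- Include children with at least one avatrombopag dose.
- Start at each child's first avatrombopag dose: Core Day 1 if randomised to avatrombopag, first Extension dose if randomised to placebo.
- Count only avatrombopag tablets and capsules in duration, total dosage and weekly average dose.
- Count as TEAEs only events on or after that start date.

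Leave the Core Phase by-treatment tables unchanged. Leave the compliance formula unchanged too, with assigned units taken over planned units and placebo included. Simply setting placebo dosage to zero in the shared total would give placebo children 0% Core Phase compliance, and SAP 6.6 lists compliance among its example per-protocol criteria.

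The cost is a few lines of SAP text and one derived treatment-start flag, with no new data and no change to conduct. It should be done before database lock, since SAP 7 treats analyses designed afterwards as post hoc.

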10.2 Adverse Events of Special Interest

The purpose for specifying AESI is to enable further characterization of the clinical course and management of specific events. The Investigator will monitor each subject for clinical and laboratory evidence of pre-defined AESIs throughout their participation in the study, and will report all AESIs listed below within the same timeframe as an SAE (Section 10.4). An AESI may or may not be the consequence of treatment with avatrombopag.

The AESI defined in this protocol include:

- Thromboembolic events (any thrombotic or embolic event, whether arterial or venous).
- Bleeding events (any clinically significant blood loss [e.g., WHO Grade 2 or higher]).

These events will be recorded on the AE eCRF page. The Investigator will assess and record any additional information on the AESI in detail on a SAE form (whether or not the event meets seriousness criteria in Section 10.3), to be submitted within 24 hours of awareness of the event. During the course of the study, additional AESI may be identified and communicated by the Sponsor.

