3.2.2 Safety Endpoints

- Incidence of AEs, SAEs, and AEs of special interest (AESI) during the study
- Measurement of clinical laboratory tests during the study
- Measurement of vital signs during the study

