4.3.2 Baseline for Other Evaluations

For all other evaluations (except WHO bleeding scale), baseline is defined as the most recent non-missing measurement prior to first dose date/time of study drug in the randomized control period.

For WHO bleeding scale, baseline is defined as the most severe (worst) bleeding event recorded prior to the first dose date/time of study drug in the randomized control period.

Grade 0	No bleeding
Grade 1	Petechial bleeding
Grade 2	Mild blood loss (clinically significant)
Grade 3	Gross blood loss
Grade 4	Debilitating blood loss

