5. PLANNED ANALYSIS

5.1 Changes from Planned Analyses in the Protocol

An exploratory efficacy endpoint was included which was not detailed in the protocol: Month 3 durable platelet response defined as the proportion of subjects achieving at least 3 out of 4 weekly platelet counts $\geq 50 \times 10^9$ /L during the last 4 weeks of the 12 week Treatment Period in the Core Phase in the absence of rescue medication.

Bleeding Adverse Events of Special Interest identified using a MedDRA SMQ were further defined as clinically significant blood loss using reported CTCAE grades instead of WHO bleeding grades, as WHO bleeding grades collected at study visits are not linked to individual adverse events.

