Alternative Primary Efficacy Endpoint • Platelet response defined as proportion of subjects for whom at least 2 consecutive platelet assessments are ≥50×10 ⁹ /L during last 8 weeks of the 12 week treatment in the Core Phase in the absence of rescue medication	CMH test

Secondary Efficacy Endpoints

Percentage of weeks subjects have a platelet count $\geq 50 \times 10^9 / L$ during 12 weeks of treatment in the Core Phase, in the absence of rescue therapy. Denominator for this calculation is based on the number of weeks the subject was on treatment (up to 12 weeks)

CMH test

tests

Nonparametric

Wilcoxon Rank Sum

Platelet response at Day 8 (defined by the proportion of subjects with a platelet count $\geq 50 \times 10^9 / L$ at Day 8, in the absence of rescue therapy)

Endpoint	Analysis Method
• Percentage of weeks subjects have a platelet count between ≥50×10 ⁹ /L and ≤150×10 ⁹ /L, during 12 weeks of treatment in the Core Phase, in the absence of rescue therapy. Denominator for this calculation is based on the number of weeks the subject was on treatment (up to 12 weeks)	Nonparametric Wilcoxon Rank Sum tests
• Proportion of subjects who require rescue medications during 12 weeks of treatment in the Core Phase of the study	CMH test
• Overall incidence and incidence of severe bleeding symptoms (scale 3 and 4) associated with ITP measured using the WHO Bleeding Scale	CMH test
Exploratory Efficacy Endpoint	
• Month 3 durable platelet response defined as the proportion of subjects achieving at least 3 out of 4 weekly platelet counts ≥50×10 ⁹ /L during the last 4 weeks of the 12 week Treatment Period in the Core Phase in the absence of rescue medication	CMH test

Note: Fisher's exact test will be used if CMH test fails.

If the test of the treatment effect on the primary efficacy endpoint is statistically significant, the statistical tests on the secondary efficacy endpoints will be considered inferential; otherwise, the tests will be considered descriptive and no statistical inference can be drawn with regards to the secondary efficacy endpoints.

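### The SAP counts bleeding AESIs only from CTCAE Grade 3, while the protocol's example threshold is WHO Grade 2; the SAP's list of changes does not state or justify the cut-off

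*SAP*

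**What the plan says.** Protocol section 10.2 lists two AESI categories. The second is "Bleeding events (any clinically significant blood loss [e.g., WHO Grade 2 or higher". On recording, the section says "These events will be recorded on the AE eCRF page". It also requires the details on an SAE form within 24 hours, whether or not the event is serious.

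Both documents print the WHO bleeding scale (protocol Appendix C; SAP sections 4.3.2 and 7.3.3). Grade 2 on that scale reads "Mild blood loss (clinically significant" and is the lowest grade with that label.

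SAP section 7.5.2 defines the bleeding category as "Any clinically significant blood loss [e.g., bleeding events with CTCAE grade 3" or above, programmed as an AE severity value of at least 3 within the Haemorrhage SMQ excluding laboratory terms. The AESI line of the overall TEAE summary is unqualified: "CTCAE Grade ≥3 Bleeding events".

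SAP section 5.1 declares that CTCAE grades replace WHO grades for this category, "as WHO bleeding grades collected at study visits are not linked to individual adverse events". It names no CTCAE threshold.

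SAP section 3.2.2 has as a safety endpoint "Incidence of AEs, SAEs, and AEs of special interest (AESI) during the study".

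**The concern.** The SAP keeps the protocol's notion of clinically significant bleeding but attaches it to what appears to be a higher threshold. A bleed that an investigator must report as an AESI under protocol 10.2 can then fail the SAP's AESI rule because it is graded below CTCAE 3.

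Three outputs are affected: the line for any AESI in the overall TEAE summary, the AESI table by category and preferred term, and the AESI listing. The AESIs that sites reported and the AESIs that the study report presents would not reconcile, on a safety endpoint named in both documents.

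There is a second cost. SAP 7.5.2 already lists all Grade 3 to 5 TEAEs separately, so a bleeding AESI listing limited to Grade 3 or higher largely repeats it. That weakens the purpose protocol 10.2 gives for AESIs, which is to characterise the course and management of particular events more closely.

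**Working it through.** There is no plan figure to reproduce, since the point concerns a definition. The check sets the texts side by side.

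**1. The rule in each document**

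| | Protocol 10.2 | SAP 7.5.2 |
|---|---|---|
| Concept | Clinically significant blood loss | The same |
| Example or rule | WHO Grade 2 or higher | CTCAE Grade 3 or higher, severity value at least 3 |
| Source of events | Investigator-identified, reported event by event | Haemorrhage SMQ terms passing the severity filter |
| Summary line | – | Grade 3 or higher, unqualified |

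The SAP's category definition introduces the grade as an example. Its only programmable rule is still the severity filter, and the summary line drops the example wording.

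**2. Is the SAP rule narrower?** WHO and CTCAE are different scales, so 3 against 2 does not settle it. The documents' wording points to yes. The protocol's threshold starts at bleeding described as mild. Protocol 10.1.2.1 equates CTCAE Grade 3 with severe, incapacitating symptoms and Grade 2 with moderate ones. That text governs only events not listed in CTCAE, so it is indicative and not decisive.

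**3. Does the reason in SAP 5.1 cover the cut-off?** The reason is that WHO grades taken at visits cannot be tied to individual events. CTCAE grades are recorded per event, so using them solves that problem at any cut-off, Grade 2 as well as Grade 3. The reason also leaves the investigators' own AESI reports available, because protocol 10.2 has them recorded per event.

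**4. Does another output supply the missing count?**

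- SAP 7.4, Table 3 tests "Overall incidence and incidence of severe bleeding symptoms (scale 3 and 4" on the WHO scale, that is, any bleeding and Grades 3–4. WHO Grade 2 or higher is not analysed.
- SAP 7.4 otherwise summarises WHO grade by visit, which does not give the number of subjects ever reaching Grade 2.
- SAP 4.2 mentions worst post-baseline analyses in general terms, but no section specifies one for WHO grade.
- The TEAE table by maximum grade shows Grade 2 bleeds term by term. A subject with two bleeding terms counts under both, so the rows cannot be added to give subjects.
- The AE listing holds the individual events but no count.

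No specified output therefore gives the number of subjects with at least one bleed at the protocol's threshold.

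**5. Size, as illustration only.** The documents contain no grade distribution. Protocol Table 1 gives epistaxis in 19% of adults on avatrombopag, and 54 subjects are planned on avatrombopag here.

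Expected subjects with epistaxis: 54 × 0.19 = 10.3.

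| Assumed share with CTCAE Grade 2 as worst grade | Subjects absent from AESI outputs for this term |
|---|---|
| 0% | 10.3 × 0 = 0 |
| 25% | 10.3 × 0.25 = 2.6 |
| 50% | 10.3 × 0.50 = 5.1 |

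The shares are assumptions. The table also supposes that each such epistaxis would be an AESI under protocol 10.2. Adult exposure was a median of 7 months against 12 weeks in the Core Phase, so the true figure may be lower.

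**The case against.** The case for leaving the SAP as it is runs as follows.

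- **The change is disclosed.** Section 5.1 declares the new scale with a fair reason, and the Grade 3 threshold appears twice in section 7.5.2. This is right about the scale. What is missing is a statement of and reason for the threshold in the section that exists to record departures from the protocol.
- **Both definitions give the grade only as an example, and the listing entry repeats no grade limit.** This is true of the text. In practice the severity filter defines the category, and nothing else in the SAP would bring a Grade 2 bleed into an AESI output.
- **The narrowing is not quantified.** There is no mapping between the scales, the illustration rests on assumed shares, and protocol 10.1 tells sites not to report events of disease progression as AEs unless they are unusual, which may limit which bleeds become AEs at all. All of this stands. It limits the size of the effect but does not remove the mismatch in definition.
- **Nothing is lost.** Lower-grade bleeds remain in the TEAE tables, the AE listing and the WHO summaries, expedited reporting is unchanged, and the AESI output is descriptive. This also stands, and it is why the point is moderate. The per-subject count at the protocol's threshold is still absent.
- **CTCAE Grade 2 is itself only an approximation, and the CRF may carry no AESI flag.** Both are fair. They argue for reporting by grade alongside the investigators' own AESIs, and for saying openly that the scales are not interchangeable.

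**Conclusion.** The concern holds. SAP 7.5.2 departs from protocol 10.2 in its operational threshold for bleeding AESIs, and SAP 5.1 justifies the change of scale but not the cut-off. Followed as written, the plan can leave bleeds reported as AESIs out of three AESI outputs, with no substitute count of subjects at the protocol's threshold.

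How many subjects this affects is unknown. The conclusion does not depend on the epistaxis illustration. It rests on the two definitions and on reading the severity filter as the rule that will be programmed. That the SAP rule is narrower is strongly suggested by the documents' wording, but without a mapping between the scales its extent cannot be shown.

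This should be corrected before database lock. It affects the completeness and reconcilability of a safety endpoint and does not touch any efficacy test.

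**What to change.** In SAP 7.5.2, in both the category definition and the overall summary line:

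- tabulate the bleeding AESIs that investigators reported under protocol 10.2, and/or Haemorrhage SMQ events (excluding laboratory terms) at CTCAE Grade 2 or higher, shown by grade;
- keep CTCAE Grade 3 or higher as a separate row.

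In SAP 5.1, state the cut-off and the reason for it. Add that WHO and CTCAE grades are not interchangeable, so a row at CTCAE Grade 2 or higher approximates the protocol definition and does not reproduce it. If the sponsor wants Grade 3 or higher as the headline, section 5.1 still needs to state and justify it.

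The cost is SAP wording, a little extra programming and a longer AESI table. If the AE eCRF page carries no AESI flag, the investigator-reported events must be identified from the SAE forms.
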